## Research Summary – Inhaled Pulmonary Vasodilators in Thoracic Transplantation & LVAD Surgery

hours after lung transplantation. The primary endpoint for the comparison of efficacy in LVAD patients will be incidence of moderate or severe RV failure according to Interagency Registry for Mechanically Assisted Circulatory Support (INTERMACS) scoring. The primary endpoint for the comparison of efficacy in the heart transplant subset will be the incidence rate of RVAD insertion. Secondary endpoints related to clinical outcomes for all populations will be duration of postoperative mechanical ventilation, ICU Length of Stay (LOS), hospital LOS, incidence of acute kidney injury, incidence of in-hospital mortality, as well as postoperative mortality at 30-days, 90-days, and 1-year after operation (Table 1).

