**11. Data Analysis & Statistical Considerations:** Summary statistics will be computed for demographic, clinical, and outcome variables in the form of frequencies (percentage) for categorical variables and mean (standard deviation) for continuous variables for each arm. Univariate analysis will be performed to compare the difference of each variable between treatment groups by chi-square or Fisher exact tests for categorical variables, and t-tests or Wilcoxon Rank-Sum tests for continuous variables depending on data normality. The univariate results for the outcome variables will provide information on iNO treatment effect in comparison to iEPO without taking into account other potential confounding factors. All non-outcome variables meeting  $p < 0.15$  association with treatment group will be considered for variable selection to build a multivariable regression model. For each outcome of interest, we will start with a regression model (logistic regression for binary outcomes or generalized linear model for continuous outcomes) with all variables selected from univariate analysis described above. Based on stepwise variable selection, we will determine the final set of covariates to be included in the final multivariable model to test the treatment group effect. Based on the analysis results, we will be able to understand if iNO is equivalent to iEPO (no significant difference) or significantly better or worse than iEPO (significant treatment effect) to address the efficacy of iNO for Aim 1. Several of secondary measures will be obtained over time. We will apply generalized mixed model to take into account the repeated measures over time to test for treatment effect. In the case of patients have switched to the other arm due to clinical decision, we will conduct the primary analysis based on the intent to treat (ITT) without reclassifying treatment assignment. In addition, protocol analysis, where only patients follow the protocol assignment are included will also be conducted to verify ITT results. For Aim 2 to compare cost capture analysis, the comparison of cost measures between two groups will be tested by two sample t-test.

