Based on recent *annual* operations, approximately 120 LVAD implantations, 60 heart transplantations, and 110 Lung transplantations were performed at Duke University Hospital during FY 2014 – 2015. This study has been individually powered to primary endpoints for each arm (Table 1) and the duration of study enrollment has been determined according to annual operations and sample-size calculations. We estimated sample size based on equivalence test of the incidence rates of a binary outcome (e.g. PGD grade 3 (PGD-3)) of two treatment groups as an illustration. Assuming the incidence rate of PGD-3 under iEPO treatment is 0.35 and acceptable margin of the equivalence is  $\pm 0.19$ , we will need 224 patients to have 80% power to detect an actual difference at 0.05 between two treatment group under this margin. This implies that the acceptable range of incidence rate for iNO treatment is from 0.21 to 0.59. Based on this estimate, we propose to enroll 200 lung transplant patients and 224 LVAD and heart transplant patients ( $n = 424$ ) over a period of 24 to 36 months; the exact time point for trial culmination between 24 and 36 months will be dependent on enrollment rate. There will be a 50% randomization rate for each inhaled agent such that 212 patients will receive iEPO and 212 patients will receive iNO.

**12. Data & Safety Monitoring:** The proposal is not introducing a new medication that has not been utilized by our group and safety has been established for this patient population through clinical practice and medication usage. Safety will, however, be determined by assessing reported, rare, adverse effects of iNO (systemic hypotension, methemoglobinemia, and rebound pulmonary hypertension after appropriate weaning) and iEPO (systemic hypotension, non-surgical bleeding related to thrombocytopenia, flushing, and rebound pulmonary hypertension after appropriate weaning) in order to accurately monitor adverse events (AE) during this study. The PI will review and sign off on AE's as they occur and perform a quarterly review and determine if AE's are related to the study or otherwise. AE's will be reported to the IRB per HRPP policies.

*Stopping Rule:* Subjects who meet the stopping criteria in section 4 continued to be enrolled and followed for primary outcome analysis. See section 4 for stopping criteria.

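### The stepwise logistic model that tests RVAD insertion in heart transplants makes no provision for an arm with no events, and the plan does not say which test then decides

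*Combined protocol and SAP*

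**What the plan says.** Section 4 (Measured Outcomes) gives each population its own primary endpoint. For heart transplants: "The primary endpoint for the comparison of efficacy in the heart transplant subset will be the incidence rate of RVAD insertion". LVAD patients have a different one, INTERMACS moderate or severe RV failure. Table 1 lists the two as 2a and 2b of a single cardiac population of 224.

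Section 11 plans two analyses of a binary outcome. The first is univariate, "by chi-square or Fisher exact tests for categorical variables", and is described as giving information on the treatment effect without allowance for confounders. The second is a logistic model for each outcome of interest, with covariates chosen stepwise: "we will determine the final set of covariates to be included in the final multivariable model to test the treatment group effect". From the results the investigators expect to "understand if iNO is equivalent to iEPO (no significant difference"), or else to find a significant difference in either direction.

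Section 11 does not name the test statistic for the logistic model. It does not say what happens if an arm has no events, or which analysis prevails if the two disagree. The sample-size paragraph uses severe PGD as its illustration. It gives no RVAD rate, no RVAD margin and no separate number of heart transplants.

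**The concern.** RVAD insertion may be uncommon, and the heart-transplant subset is small, so one arm could have no events. Ordinary maximum-likelihood logistic regression then has no finite odds ratio. The Wald test, which is the usual default output, returns a p-value near 1 however many events the other arm has. Under a rule that equates non-significance with equivalence, the most one-sided result possible on a primary endpoint could be taken as support for equivalence. If both arms are empty there is no estimate at all. Other sparse binary outcomes within a population, such as early mortality, are exposed in the same way.

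**Working it through.** **The plan's own figure.** There is none for RVAD insertion. The 224 in section 11 comes from the severe-PGD illustration (rate 0.35, margin ±0.19) and does not bear on this check.

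**Inputs.**
- Cardiac patients: 224 (section 11, "we propose to enroll 200 lung transplant patients and 224 LVAD and heart transplant patients").
- Annual volumes: "approximately 120 LVAD implantations, 60 heart transplantations, and 110 Lung transplantations" (section 11).
- Allocation: 1:1 ("There will be a 50% randomization rate for each inhaled agent").
- Assumed, because not stated: enrolment in proportion to volume, two-sided 0.05, no dropout, and RVAD rates from 2% to 10%.

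**Size of the subset.** 224 × 60/(60 + 120) = 74.7, about 75, or 37 versus 38.

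**Wald test.** With a of 37 and b of 38 events, the log odds ratio is ln[b(37 − a)/(a(38 − b))] and its variance is 1/a + 1/(37 − a) + 1/b + 1/(38 − b). At a = 0 both are infinite. Fitted by software, 0/37 versus 8/38 gives a coefficient of 22.2, a standard error of about 13,063 and p = 0.9986. Adding two noise covariates (300 runs) leaves the median p at 0.9986.

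**Other tests of the same 0/37 versus 8/38.**
- Fisher: C(38,8)/C(75,8) + C(37,8)/C(75,8) = 0.0029 + 0.0023 = 0.0052.
- Chi-square: 0.0031 (0.0099 with continuity correction).
- Likelihood ratio: 2 × {[8 ln(8/38) + 30 ln(30/38)] − [8 ln(8/75) + 67 ln(67/75)]} = 2 × (−19.56 + 25.46) = 11.8 on 1 df, p = 0.0006.
- Firth penalised likelihood ratio: 0.0023.

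**One event instead of none.** For 1 versus 8, ln(8 × 36/30) = 2.26 and the standard error is √(1 + 1/36 + 1/8 + 1/30) = 1.09, so p = 0.038. The failure is specific to a zero cell.

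**A less extreme split.** For 0 versus 5, Wald p is about 1, Fisher p is 0.054, Firth p is 0.024 and likelihood-ratio p is 0.0075. The conclusion depends on a choice the plan leaves open.

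**How often an arm is empty at equal rates.** The formula is (1 − r)^37 + (1 − r)^38 − (1 − r)^75. At r = 2% this is 0.474 + 0.464 − 0.220 = 72%. At 3%, 5% and 10% it is 54%, 27% and 4%.

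**Power at a true difference of 0.19.** Binomial enumeration of the unadjusted comparison, with the lower rate in the arm of 37 and Wald p set to 1 in a zero cell:

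| True rates | Wald | Fisher | Firth |
|---|---|---|---|
| 2% vs 21% | 26% | 66% | 75% |
| 5% vs 24% | 46% | 57% | 64% |
| 10% vs 29% | 51% | 48% | 54% |

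The 0.19 is borrowed from the PGD illustration only to fix a scale.

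**Type I error.** The likelihood-ratio test rejects in 9.1% of trials at 5% versus 5%. Firth rejects in 0.3% to 4.3% at equal rates of 2% to 10%.

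**The case against.** The strongest reply is that section 11 never names the Wald test, and that it already requires a chi-square or Fisher test of the same outcome. For 0 versus 8 that test gives p between 0.003 and 0.010, and the sentence on interpretation refers to the analysis results generally. A reader might infer that the plan would simply declare 0 versus 8 equivalent. The documents do not support that: the conflict would be visible. What remains is that the plan names the multivariable model as the test of treatment and has no rule for disagreement, so any resolution would be made after seeing the data. Switching to the likelihood-ratio test does not solve it, given that test's type I error.

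A reader might also take 72%, 54%, 27% and 4% as the frequency of wrong conclusions. They are computed at equal rates, where non-significance is the right answer. The chance of an empty arm together with Fisher p below 0.05 is only 0.04% to 0.9% over the same rates. The harm arises when true rates differ and the lower one is near zero.

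Nor can it be said that the model is unable to estimate this endpoint in general: with one event in the smaller count it does so.

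Finally, Table 1 groups heart transplant with LVAD, and a combined analysis of 224 would make an empty arm less likely. That is possible, but section 4 assigns RVAD insertion to the heart-transplant subset and gives LVAD patients another endpoint, which favours a separate analysis.

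**Conclusion.** The concern holds conditionally. If heart transplants are analysed alone and one arm has no RVADs, the stated model gives no finite treatment estimate, its usual p-value is uninformative, and the plan does not say what decides instead. Where the lower true rate is about 2%, reliance on the Wald test costs 40 percentage points of power against Fisher (26% against 66%). At 5% the cost is 11 points (46% against 57%), and by 10% it is gone. These sizes rest on assumed RVAD rates, an inferred 75 patients and a borrowed difference of 0.19, none of which the documents state for this endpoint.

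The rule that non-significance means equivalence compounds the problem and outlasts a change of test: 0 versus 5, with Fisher p = 0.054, would still be called equivalent. Replacing the test alone is therefore not enough.

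**What to change.** In section 11, take RVAD insertion, and any other binary outcome too sparse for the model (for example, fewer than about 10 events per model term), out of the stepwise logistic procedure. State that the deciding analysis is the unadjusted risk difference with a Miettinen-Nurminen or exact confidence interval, judged against a margin set in advance for that endpoint and not by the absence of significance. If an adjusted estimate is wanted, specify Firth logistic regression with a profile-likelihood interval and covariates fixed in advance. State also that heart transplants are analysed separately for this endpoint, if that is the intention.

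The cost is a change of wording, the work of justifying an RVAD margin, and standard software. The RVAD result would be unadjusted or lightly adjusted, and with about 75 patients it may often be inconclusive.

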### Aim II – Cost-Capture Analysis.

In parallel with the design & procedures of *Aim I*, the cost capture analysis component will be essential in order to better gauge the cost due to duration of administration (variable cost) according to each inhaled PVD. Established clinical criteria specific to each group (lung transplantation vs. heart transplantation/LVAD implantation) have been developed to determine the inception of protocolized PVD weaning. Weaning medications according to established protocols will allow for accurate interpretation of the comparative length of therapy between iNO and iEPO and help prevent erroneous PVD usage without criteria for discontinuation. Secondary resource utilization will be documented by respiratory care services and itemized cost sheets will be developed.

### Subject Groups

Inhaled PVD therapy is administered to every patient undergoing thoracic transplantation and LVAD implantation at our institution and each patient is eligible for enrollment. Over a 3-year period (1 year for follow-up) we will prospectively enroll 200 lung transplant subjects and 224 heart transplant or LVAD implantation patients who will be informed and consented prior to their scheduled procedure. Potential subjects will be under the care of 1 or more investigators in this study. Consented subjects will be randomly assigned to 1 of 2 groups, iNO vs iEPO, to be initiated in the OR on the day of the operation based on accepted standard of practice and study protocol. Medication administration will be double-blinded, such that neither the surgical nor anesthesiology teams will be notified of the inhaled agent to which the patient has been randomized. Ability to unblind the delivery system will be made available to both teams if required to preserve optimal patient care. As per our standard practice, respiratory care services will manage the initiation and maintenance of inhaled PVDs in the OR and ICU, and these personnel will be the only practitioners notified of the actual delivered medication during study blinding.

### Exclusion Criteria

- Combined Organ Transplantation (Heart-Lung, Heart-Liver, Heart-Kidney)
- Age < 18 years old
- Pregnancy (females of child bearing potential will receive pregnancy testing prior to cardiothoracic surgery as a standard of care)
- Known allergy to prostaglandin (rare)
- Refusal of blood products due to personal or religious preference.
- Subject is enrolled in another study protocol, which does not allow randomization of PVD therapy
- Heart transplant or durable LVAD recipients with adult congenital heart disease (CHD)
- Caveat: Does NOT meet exclusion criteria if the scheduled heart transplant or LVAD implantation is due to heart failure from a *previous heart transplantation* related to CHD, performed more than 90 days previous to the date of trial enrollment
- Patient is scheduled to undergo lung transplantation but has undergone heart transplantation in the previous 90 days
- Patient is scheduled to undergo durable LVAD implantation but has undergone heart transplantation in the previous 90 days
- Patient is scheduled to undergo heart transplantation but has undergone lung transplantation in the previous 90 days
- Patients with preoperative VV ECMO as a bridge to lung transplantation
- 

Stopping Criteria – In the event the following criteria are met and the clinical team is in agreement, subjects will be weaned off of their iPVD per institutional standard iPVD weaning practice. If adverse events are encountered, the drug will be immediately stopped without weaning.

- Venoaerterial (VA) ECMO insertion remains at end of operation
- VA ECMO insertion is performed postoperatively in the ICU
- LVEF < 30% on echocardiogram at the end of the operation for heart and lung transplant subjects

## Research Summary – Inhaled Pulmonary Vasodilators in Thoracic Transplantation & LVAD Surgery

- LVEF < 30% for heart and lung transplant subjects on echocardiogram noted postoperative in the ICU
- Inhaled pulmonary vasodilation is halted for reasons other than standard weaning ordered by the clinical care team
- Adverse events related to the INO or EPO that affect the subject's welfare

### Data Collection

*Secondary measures will be hemodynamic variables* (similar to those measured in Table 2) such as transesophageal echocardiographic (TEE) evaluation of RV function based on stand-of-practice protocol, intravenous administration of inotropes, serial measures of postoperative serum creatinine and GFR, resolution of elevated liver function tests (heart failure patients, illustrates improvement in RV function), incidence of thrombocytopenia (platelet count < 150 x 10^9/L) and trajectory of resolution, as well as ventilation-to-perfusion matching (arterial oxygen tension, PaO2; arterial carbon dioxide tension, PaCO2; and fraction of inspired oxygen, FiO2). Variables will be recorded at designated time points during the entire duration of administration – from initiation in the operating room to cessation in the ICU. These time points include: Intraoperative before surgical incision, time = 0 (initiation of PVD), 30 minutes, 2 hours, 6 hours, 12 hours, 18 hours, 24 hours, and every 6 hours up through 72 hours after initiation. These secondary measures will be obtained up through 72 hours after initiation regardless of cessation or continuation of the inhaled PVD. After 72 hours, increments of every 12 hours thereafter will be assessed if PVD administration continues. Ventilation and perfusion nuclear scans will be obtained and recorded per standard clinical practice for each group of lung transplant recipients. Established protocols with criteria for initiation of medication weaning have been created according to each medication based on individual pharmacokinetic properties. Once established criteria are met, weaning of each inhaled PVD will begin and continue until the medication is terminated according to standardized weaning protocols established for lung transplant patients and heart transplant/LVAD patients.

*Subject follow up.* Subject will be contacted by phone by a member of the research team and be asked a short series of questions to assess their current medical condition and any changes since surgery at 30-days (± 3 days), 90-days (± 5 days), and 1-year (± 7 days) after surgery completion date. The phone follow-up should take approximately 5 minutes of the subject's time. If subjects have been admitted to a hospital outside of Duke Health after surgery they will be asked to sign an authorization of release to provide us permission to obtain medical information related to their hospitalization.

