### 3. Background & Significance:

**Introduction.** Inhaled Nitric Oxide (iNO) is a selective pulmonary vasodilator (PVD) with FDA-approval in the neonatal population alone. In adult patients, iNO is used off-label to treat pulmonary hypertension, right ventricular (RV) failure, and ventilation-to-perfusion mismatch. Adult patients who undergo durable LVAD implantation (e.g. Heartware®, Heartmate 2®, or Heartmate 3®) or cardiac transplantation for end-stage heart failure or those that have endured lung transplantation as a result of end-stage lung disease, compose the largest subpopulation which receives PVD therapy at Duke University Hospital. Intravenous Epoprostenol is FDA approved for adult patients with pulmonary hypertension and is the only agent which has displayed mortality benefit in these patients. The inhaled formulation of Epoprostenol (iEPO) was developed in order to maintain efficacy and avoid the systemic side effects of vasodilation and thrombocytopenia. Inhaled iEPO is used off-label in our cardiothoracic surgical patients for new-onset perioperative pulmonary arterial hypertension (PAH), known preoperative PAH, RV dysfunction with LVEF > 35-40%, and promotion of ventilation to perfusion matching through alveolar deposition of the prostanoid compound and vasodilation of the intimately associated intra-acinar pulmonary arteries. This vasodilation can decrease pulmonary vascular resistance and can improve oxygenation while avoiding systemic effects commonly seen in the intravenous formulation. iEPO has been introduced in the cardiothoracic operating rooms (OR) and ICU as a cost-conscious alternative medication to iNO. iEPO may display an equivalent efficacy profile to iNO for pulmonary vasodilation and oxygenation and have a similar impact on clinical outcomes. For the purposes of this writing, thoracic transplantation will refer to both heart and lung transplantation.

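### Thrombocytopenia is counted as any platelet count below 150 x 10^9/L with no reference to the pre-drug count, which dilutes any drug effect; the population for its resolution is not stated

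*Combined protocol and SAP*

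**What the plan says.** The Data Collection section of the protocol names two linked platelet measures among its secondary measures. The first is "incidence of thrombocytopenia (platelet count < 150 x 10"^9/L); the second is its course of recovery, "and trajectory of resolution, as well as ventilation-to-perfusion matching". The first is a fixed cut, without new-onset wording or any change from baseline. The second has no population, start point or recovery threshold.

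The same section schedules a pre-drug value: "These time points include: Intraoperative before surgical incision, time = 0 (initiation of PVD), 30 minutes, 2 hours, 6 hours", and so on to 72 hours. It adds: "These secondary measures will be obtained up through 72 hours after initiation regardless of cessation or continuation of the inhaled PVD".

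The Exclusion Criteria contain no platelet limit. The nearest item is "Refusal of blood products due to personal or religious preference".

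Section 11 says of secondary measures taken over time: "We will apply generalized mixed model to take into account the repeated measures over time to test for treatment effect". It does not link that model to platelets, restrict it to cases or name a baseline platelet term. Its general covariate rule admits a variable only if it is associated with treatment group at p < 0.15, followed by stepwise selection.

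Platelets matter to the protocol's own rationale. Section 3 says the inhaled form was developed to "avoid the systemic side effects of vasodilation and thrombocytopenia", and section 12 lists "non-surgical bleeding related to thrombocytopenia" among the epoprostenol effects to be monitored.

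**The concern.** As written, the measure records whether a patient ever had a low count, not whether one developed after drug. A patient who arrives at 140 is a case at the first draw. A patient who falls from 400 to 155 is not.

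Two losses follow. Patients already low are cases in both arms whatever the drug does, so they shrink the difference between arms. Cutting a count into yes or no also discards the size of the fall. Both push the comparison towards no significant difference. For the efficacy question of Aim 1, section 11 reads that result as equivalence, and it offers no other reading for secondary or safety measures. An insensitive platelet measure could therefore be taken as reassurance.

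Resolution raises a separate issue. The word has meaning only for someone who has had a low count, and some patients will first become low after drug start. If the arms were compared only among such patients, the groups compared could be partly formed by the drug, and the protection of randomisation would be lost.

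**Working it through.** The plan gives no platelet rate, variability or power, so there is no figure to reproduce. From the documents: the cut of 150, allocation of 212 per arm (section 11), the measurement schedule and the p < 0.15 screen. Everything else below is an assumption for illustration, with all 424 patients analysed together.

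**Step 1. Can prevalent cases enter, and does the analysis correct for them?** They can enter, because no exclusion concerns platelets. The pre-drug value should exist, because pre-incision and time-0 points are scheduled, but no rule says how to use it. Section 11's screen does not repair this. Under randomisation a baseline variable shows association with arm at p < 0.15 about 15% of the time, so baseline platelets would be left out about 1 - 0.15 = 85% of the time, however well they predict later counts.

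**Step 2. Dilution by prevalent cases.** Let b be the share already below 150 and p the new-onset risk. Then P(case) = b + (1 - b)p, and the risk difference (RD) between arms is (1 - b)(p2 - p1). Assume p1 = 0.30 and p2 = 0.40. Power = Phi[(d - 1.96 se0)/se1], where d is the difference in case rates, se0 its standard error with pooled variance and se1 with unpooled variance.

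Example, b = 0.30: rates are 0.30 + 0.70 x 0.30 = 0.51 and 0.30 + 0.70 x 0.40 = 0.58; d = 0.07; se0 = 0.0484; se1 = 0.0482; power 0.30. For new onset among those at risk, n per arm is 212(1 - b) and the difference stays 0.10.

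| b | Any-low rates | RD | Power, any low | Power, new onset |
|---|---|---|---|---|
| 0 | 0.30 v 0.40 | 0.10 | 0.58 | 0.58 |
| 0.1 | 0.37 v 0.46 | 0.09 | 0.47 | 0.54 |
| 0.3 | 0.51 v 0.58 | 0.07 | 0.30 | 0.44 |
| 0.5 | 0.65 v 0.70 | 0.05 | 0.19 | 0.33 |

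**Step 3. Loss from the cut itself.** Assume a normal nadir with mean m in one arm and m - 15 in the other. The rates below 150 are Phi[(150 - m)/SD] and Phi[(165 - m)/SD]. Power for the cut = Phi[d/se1 - 1.96]. Power for the mean nadir = Phi[15/(SD x sqrt(2/212)) - 1.96].

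- SD 40: standard error 3.885; 15/3.885 = 3.86; power 97%.
- SD 60: standard error 5.828; 15/5.828 = 2.57; power 73%.

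| Mean nadir | Rates, SD 40 | Power of cut, SD 40 | Power of cut, SD 60 |
|---|---|---|---|
| 80 | 96% v 98% | 30% | 32% |
| 100 | 89% v 95% | 54% | 41% |
| 120 | 77% v 87% | 74% | 48% |
| 140 | 60% v 73% | 85% | 53% |
| 150 | 50% v 65% | 87% | 54% |
| 160 | 40% v 55% | 87% | 54% |
| 180 | 23% v 35% | 83% | 52% |

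With a shift of -10 at SD 40, the mean nadir has 73% power and the cut 17% to 54% over the same means. The cut has lower power in every case run. This step does not model prevalent cases, and it does not credit the further gain from adjusting for the pre-drug count.

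**Step 4. Resolution.** No arithmetic applies. Data Collection gives no population. Section 11's mixed model, if applied to platelets, could cover everyone randomised. The text therefore permits both an all-patient analysis and one confined to patients with a low count, and it chooses neither.

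**The case against.** Incidence ordinarily means new occurrence, and pre-drug values are scheduled, so an analyst might set prevalent cases aside without being told. That is fair. The misclassification follows from a literal reading and is not a stated rule. But the definition in brackets is the only operational text, and it does not say this.

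A reader might infer that resolution is to be studied only in patients who became low after randomisation. The documents do not say so. If any count below 150 makes a case, resolution would also cover patients low before drug, and section 11's mixed model is compatible with analysing all patients. What stands is that the population is undefined and that one natural choice would be unsound.

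A reader might also infer that the measure favours one drug. With 1:1 randomisation, prevalent cases are expected to balance, so this does not follow.

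The power figures rest wholly on assumed inputs. Nothing in the documents shows that most patients fall below 150 after surgery, and with mean nadirs of 140 to 180 at SD 40 the cut has 83% to 87% power. The size of the loss is therefore uncertain. Its direction held throughout the range tried.

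Finally, the stakes are modest. Platelets are not among the secondary outcomes in Table 1, and section 12 monitors related bleeding as an adverse event.

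**Conclusion.** The point holds as a minor but concrete improvement. The platelet measure has no pre-drug reference, prevalent cases are not excluded, and the covariate rule would usually leave baseline platelets out. The consequence is dilution and lost power.

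On assumed inputs, a new-onset risk difference of 0.10 shrinks to 0.09, 0.07 or 0.05 if 10%, 30% or 50% of patients are already low. Separately, for a shift of -15, the cut has 30% to 87% power against 97% for the mean nadir at SD 40, and 32% to 54% against 73% at SD 60. These ranges illustrate the loss and are not estimates for this trial.

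For resolution, the supported conclusion is conditional: the population is not stated, and limiting it to patients with a low count would condition on an event that in some patients arises after drug start. Primary endpoints and sample size are not affected.

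**What to change.** In Data Collection, and by cross-reference in section 11:

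- Make the platelet measure the count from time 0 to 72 hours in all randomised patients. Use either the nadir or the serial counts in the mixed model already planned, adjusted for the pre-incision count as a pre-specified covariate outside the p < 0.15 screen.
- Report the rate below 150 x 10^9/L by arm as a description, split into present before drug and new after drug.
- Replace resolution among cases with the platelet trajectory in all randomised patients.
- Report platelet transfusion and death before 72 hours by arm, since both affect the counts.

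The cost is wording and analysis only, because the schedule already includes the pre-incision value and follow-up to 72 hours whether or not the drug continues. The downside is that the simple incidence figure becomes descriptive, and that transfusion and early death complicate reading the counts and must be shown beside them.
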